5.7 ADDITIONAL SAFETY ANALYSES	31
6 ETHICAL REVIEW & REGULATORY CONSIDERATIONS.....	32
6.1 ETHICAL REVIEW.....	32
6.2 REGULATORY CONSIDERATIONS.....	32
6.3 MONITORING PROCEDURES.....	32
6.3.1 Training of Study Site Personnel	33
6.4 INFORMED CONSENT.....	33
6.5 PROTOCOL ADHERENCE.....	33
6.6 DATA COLLECTION	33
6.7 RECORD RETENTION	34
6.8 CLINICALTRIALS.GOV.....	34
7 REFERENCES	35
8 LIST OF PROTOCOL ATTACHMENTS.....	38
8.1 PROTOCOL ATTACHMENT 1 – TIME TABLE OF STUDY PROCEDURES.....	38
8.1 PROTOCOL ATTACHMENT 2 – SCHEMA	39

Transcranial Near-Infrared Light in Healthy Subjects: a Cerebral Blood Flow Study with Diffuse Correlation Spectroscopy (NIR-flow).

1. Study Summary

Protocol #:

Study Purpose: The purpose of this study is:

- To assess the change in cerebral blood flow induced by the Transcranial Continuous and Pulse Near-Infrared Light Therapy in healthy subjects
- To correlate with cognitive performance the change in cerebral blood flow induced by the Transcranial Continuous and Pulse Near-Infrared Light Therapy in healthy subjects
- To correlate with skin pigmentation the change in cerebral blood flow induced by the Transcranial Continuous and Pulse Near-Infrared Light Therapy in healthy subjects
- To correlate with brain electrical activity the change in cerebral blood flow induced by the Transcranial Continuous and Pulse Near-Infrared Light Therapy in healthy subjects
- To assess the safety and tolerability of the Transcranial Continuous and Pulse Near-Infrared Light Therapy in healthy subjects

Trial Design: In essence, this study consists in three sequential sessions of Diffuse Correlation Spectroscopy (DCS), each one week apart, to test three different modes of intervention with Transcranial Light Therapy (TLT). Healthy subjects will receive first a session with continuous light (c-TLT), then a session with sham (s-TLT) and one session with pulse light (p-TLT). Before and after each session, subjects will undergo DCS, which will allow measuring the impact of the intervention on cerebral blood flow. We expect that out of 30 subjects enrolled 10 subjects will be eligible to complete the study. The study will be conducted in single blind.

Study Population: Subjects eligible for study participation will be healthy by Structured Clinical Interview for Diagnostic Statistical Manual-IV (SCID) criteria. Subjects will be between 18-70 years of age (have not had 71st birthday) on the date of screening. Subjects who will be permitted into the study include those who meet all the inclusion criteria and have none of the exclusion criteria.

Duration of Participation:	Subjects will be followed in the study for 5 weeks.
Endpoints:	
Engagement of cerebral blood flow – The effect of TLT on cognition will be assessed before and after each session (c-TLT, s-TLT and p-TLT) by measuring the Diffuse Correlation Spectroscopy (DCS) signal.
 
Engagement of cerebral electrical activity – The effect of TLT on brain electrical waves will be assessed before and after each session (c-TLT, s-TLT and p-TLT) by measuring the Electro-Encephalographic (EEG) signal.
 
Engagement of cognitive circuitry – The effect of TLT on working memory will be assessed immediately after each session by n-back task.
 
Safety - The safety endpoints will evaluate any reported adverse events within one week from each sessions of TLT.

Entry Criteria: Inclusion Criteria	
	
 1. Subject's age at screening will be between 18 and 70 years old (inclusive). 2. Women of child-bearing potential must use a double-barrier method for birth control (e.g. condoms plus spermicide) if sexually active. 3. Subject Informed Consent obtained in writing in compliance with local regulations prior to enrollment into this study. 4. The subject is willing to participate in this study for at least 5 weeks.
Exclusion Criteria:	
	
 1. The subject is pregnant or lactating. 2. The subject is on any psychotropic medication. 3. Psychotherapy is exclusionary unless the subject has had at least 8 weeks of treatment prior to the screening visit. 4. Any current psychiatric disorder (per SCID assessment) 5. Substance or alcohol dependence or abuse in the past 6 months. 6. History of a psychotic disorder or psychotic episode (current psychotic episode per SCID assessment). 7. Bipolar affective disorder (per SCID assessment). 8. Unstable medical or neurological illness, defined as any illness which is not well-controlled with standard-of-care medications (e.g., insulin for diabetes mellitus, HCTZ for hypertension). 9. Suicidal or homicidal ideation as determined by SCID screening.

10. The subject has a significant skin condition (i.e., hemangioma, scleroderma, psoriasis, rash, open wound or tattoo) on the subject's scalp that is found to be in proximity to any of the procedure sites.
11. The subject has an implant of any kind in the head (e.g. stent, clipped aneurysm, embolised Arteriovenous Malformation (AVM), implantable shunt – Hakim valve).
12. Any use of light-activated drugs (photodynamic therapy) within 14 days prior to study enrollment (in US: Visudine (verteporfin) – for age related macular degeneration; Aminolevulinic Acid- for actinic keratoses; Photofrin (porfimer sodium) – for esophageal cancer, non-small cell lung cancer; Levulan Kerastick (aminolevulinic acid HCl) – for actinic keratosis; 5- aminolevulinic acid (ALA)- for non-melanoma skin cancer)
13. Recent history of stroke (90 days).
14. Personality traits that rend the subject unsuitable for the study, based on the investigators' clinical judgment.

2. List of Abbreviations

ALA = 5-aminolevulinic acid
ASQ = Anxiety Symptoms Questionnaire
ATP = adenosine triphosphate
AVM = Arteriovenous Malformation
CADSS= Clinician Administered Dissociative States Scale
C-SSRS = Columbia-Suicide Severity Rating Scale
CFR = Code of Federal Regulations
CHRT = Concise Health Risk Tracking
CATSD = Center for Anxiety and Traumatic Stress Disorders
EEG = electroencephalogram
FDA = Food and Drug Administration
LED = Light Emitting Diode
HAM-D-17 = Hamilton Depression rating scale
MOCA Montreal Cognitive Assessment
MDD = Major Depressive Disorder
MGH = Massachusetts General Hospital
NEURO-QOL = Quality of Life in Neurological Disorders
TSRQ = TLT Self-Report Questionnaire
OSHA = Occupational Safety and Health Administration
PANAS = Positive and Negative Symptoms Questionnaire
PBQ = Perceptions of Blinding Questionnaire
PI = Principal Investigator at the site
SAE = Serious Adverse Event
SAFTEE-SI = Systemic Assessment for Treatment Emergent Events
SCID = Structured Clinical Interview for Diagnostic Statistical Manual-IV

SDQ = Symptoms of Depression Questionnaire

SFI = Sexual Functioning Inventory

TLT = Transcranial Light Therapy

3. Introduction

Transcranial Light Therapy (TLT) with near-infrared light has recently emerged as a potential new antidepressant treatment in both animal models¹ and human studies²⁻⁴. TLT consists of delivering invisible near-infrared radiation (NIR), or red light to the scalp of the subject, which penetrates the skull and modulates function of the adjacent cortical areas of the brain. Red and/or near-infrared light appears to increase cellular brain metabolism and neuroplasticity, and to modulate endogenous opioids, while decreasing inflammation and oxidative stress⁵⁻⁷. TLT has been shown to penetrate deeply into the cerebral cortex⁸⁻¹⁰, to modulate cortical excitability¹¹ and improve cerebral perfusion¹⁰ and oxygenation¹². Studies have suggested that it can significantly improve cognition in healthy subjects¹³⁻¹⁵, and in subjects with traumatic brain injury¹⁶⁻¹⁸. The safety of TLT has been studied in a sample of 1,410 acute stroke subjects, with no significant differences in rates of adverse events between TLT and sham exposure¹⁹⁻²¹. Converging evidence from uncontrolled studies suggests both an antidepressant and anxiolytic effect of TLT in subjects suffering from Major Depressive Disorder (MDD)²⁻⁴. It is critically important to understand the biological targets of TLT and we hypothesize that the improvement in cerebral brain flow is one of the underlying mechanism for the boost in bioenergetic metabolism leading to therapeutic effects, such as enhancement of cognitive functioning.

3.1 *Summary of Prior Clinical Experience*

We conducted two studies on the safety and efficacy of TLT delivered to the forehead (prefrontal cortex) twice a week in subjects with MDD.

ELATED-1 was a proof of concept study of 3 weeks of TLT (Neurothera - class IV laser, wavelength 808 nm; irradiance 700 mW/cm²; fluence of 84 J/cm²; total energy 2.4 kJ per session for 6 sessions) (6). All subjects (n=4) were treated with TLT. Baseline mean Hamilton Depression rating scale (HAM-D-17) scores for depression decreased from 19.8±4.4 (SD) to 13±5.35 (SD) after treatment (p=0.004).

ELATED-2 was a double-blind, randomized, controlled study of 8 weeks of TLT (Omnilux New U - LED, 830 nm; 36.2 mW/cm²; up to 65.2 J/cm²; vs. sham for 16 sessions). At endpoint, the mean HAMD-17 for depression decreased of 11.7±7.5 points (TLT, n=9) vs. 5.3±7.0 points (sham, n=9) (p=0.04); the differences were even more pronounced in the completers sample as HAMD-17 decreased of 15.7±4.4 (TLT, n=6) points vs. 6.1±7.9 points (sham, n=7) (p=0.01).

These findings suggest that TLT could be a novel intervention for subjects with MDD. Both the Laser study (ELATED-1) and the LED study (ELATED-2) were conducted by our group at Massachusetts General Hospital (MGH).

NIR-flow (the present submission) will test for the first time the biological underpinning of TLT, by focusing on the effect of TLT on cerebral blood flow.

The LiteCure® The PhotoBioModulation-1000 (TPBM-1000) device to be used in this study does not require Food and Drug Administration (FDA) approval. In fact, the TPBM-1000 device used in this study is considered a non-significant risk device because:

- TPBM-1000 dose does not exceed the Maximum Permissible Exposure (MPE) for skin – Center for Devices and Radiological Health (CDRH), 21CFR1040.10 and 21CFR1040.11;
- TPBM-1000 is substantially equivalent to the OmniLux New U device (used in ELATED-2 at MGH), which the FDA has already categorized as a non-significant risk device;
- TPBM-1000 differs from the OmniLux New U only in that it provides an additional site of irradiation – treatment is delivered to EEG sites FP1 and FP2 in addition to F3 and F4 on the forehead;
- currently FDA-cleared LED devices are typically available over-the-counter and are considered safe to use without professional supervision.

3.2 Overview of LiteCure Light Emitting Diode (LED)System

LiteCure® TPBM-1000 is a new device with the flexibility to safely deliver either continuous light (c-TLT), pulsed light (p-TLT), or sham. The TPBM-1000 device is configured for in-office use.

TPBM-1000 delivers NIR light output at 830 +/- 30 nm. The NIR output is invisible to the naked eye, thus, the device includes visual and/or audible indicators of light emission, and is designed to deliver light to EEG sites: Fp1, Fp2, F3 and F4, covering a total surface active treatment area, of 35.8 cm^2 [$(11.52 \text{ cm}^2 \times 2) + (6.38 \text{ cm}^2 \times 2)$] with an average irradiance of 54.8 mW/cm^2 and an average fluence of 65.8 J/cm^2 . While the average fluence (energy density) is comparable to the Omnilux New U, the treatment area is significantly less for the TPBM-1000 (Omnilux New $28.7 \text{ cm}^2 \times 2$, which results in less total energy delivered per session of 2.3 kJ (compared to up to 3.7 kJ for the Omnilux New U).

TPBM-1000 devices will be fabricated to deliver either c-TLT, p-TLT, or Sham (s-TLT). In simple terms, in either TLT mode the TPBM-1000 device delivers therapeutic NIR energy; in sham the device will not deliver any light energy. The apparent behavior (i.e. the performance/output of all visible and audible indicators) of the device in any of the three programmed treatment modalities will be identical, ensuring the study is blinded to the operator. In addition, because of the low average irradiances delivered in either c-TLT and p-TLT modes the subjects will not experience any heating sensation ensuring the study is single-blind. The device will shut off automatically if skin temperature above 41°C were detected.

The TPBM-1000 devices consists of a source of light, mounted on a cap, attached to a console that controls the light delivery modality: c-TLT, p-TLT, or Sham.

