4.2 Study Design

This study is a single-blind, sham-controlled, study on the use of Transcranial continuous light therapy (c-TLT) and pulse light therapy (p-TLT) as an enhancer of cerebral blood flow in healthy subjects.

We expect that out of 30 subjects enrolled 10 subjects will be eligible to complete a sequence of three sessions of Transcranial Light Treatment (TLT) and sham.

All eligible subjects will receive two TLT sessions and one of sham (s-TLT) within the course of 5 weeks. While the sequence (c-TLT, s-TLT, p-TLT) will be the same for all subjects, the subjects will be blind to the specific mode of function used in each session.

The study site (MGH) will have one Litecure device, which will recognize the subjects' codes generated by the study statistician. Only subjects will be blind to the treatment group assignment. The Sham treatment consists of applying all the procedures for the delivery of the TLT, while actually delivering no light. The blinding of the sham will be effective because the radiation is not visible and because the active therapy (continuous or pulsed) will not produce any subject-discriminable difference from sham, e.g., skin warming. The sham treatment will mimic the TLT procedure. The treatment will be bilateral and applied to the frontal areas with two application sites on the left side and two on the right side [left and right forehead centered on EEG sites on F3, F4, Fp1, Fp2]. Energy is administered with a radiation wavelength of 830 nm. The duration of irradiation is 20 minutes at each application site (the 4 sites are irradiated at the same time which is equivalent to 20 minutes of total time). The entire sessions is estimated to last about 1.5 hours. The additional time is needed to have the subject complete a urine toxicology and self-report forms, to prepare the subject, to place the necessary protections (e.g. goggles), to inspect the subject's skin, to complete DCS before and after TLT, to set the TLT devices, and to give the subject time to rest after the irradiation. TLT treatment will only be administered by licensed physicians (i.e. MDs) who are on study staff. All staff who deliver treatment must pass training that is approved by the MGH Laser Safety Committee. The treatment will follow these specifications: wavelength 830 nm; average irradiance 54.8 mW/cm²; average fluence of 65.8 J/cm² (consistently with energy density used in the ELATED-2 study at MGH with the device Omnilux New U).

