4.8.2 TLT-DCS Visits – Visits 2-4 (Weeks 2-4)

The TLT sessions will occur once weekly for three weeks at the MGH Martinos Center for Biomedical Imaging in Charlestown. Subjects missing one session will be allowed to still receive their TLT session, by shifting the overall study schedule of one week. The study PI will be an active participant in the delivery of the TLT. The PI and other collaborators from MGH CATSD will assist with the delivery of TLT. The device TPBM-1000 for the administration of the TLT will be provided by Litecure Inc. Litecure will provide training of MGH CATSD staff in the use of the device and will provide training certificates at the completion of the training.

The overall study visit is estimated to last about 1.5 hours. The TLT session is estimated to last about 50 min – 5 minutes of EEG before DCS, 10 minutes of DCS before TLT, 20 minutes of TLT, 10 minutes of DCS after TLT and 5 minutes of EEG after DCS. EEG recording will extend to cover at least part of the time devoted to the cognitive tasks. Study sessions will take place in an office dedicated to TLT treatment at MGH Martinos Center for Biomedical Imaging in Charlestown. Only the subject and the staff administering the TLT will be allowed in during the session. The subject will comfortably lie down on an exam bed or sit on a recliner. The sites of application of TLT (left and right forehead) will be inspected for any possible skin lesions (e.g. laceration or signs of inflammation) which would contraindicate the treatment. The study staff administering the TPBM device at the TLT-DCS sessions will appropriately remove any reflective objects to fall into or obstruct the path of the light energy produced by this device. Both the subject receiving the TLT and the study staff will wear protective eyewear in the form of goggles. During treatment sessions the office will be kept completely dark and a warning sign will hang at the office door. The staff will be provided training on basic safety procedures relative to the use of the device.

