The trained staff administering the TLT will use utmost care to never shine the light in or near the eyes of the subject safety goggles will be selected based on the TLT biophysical properties, in accordance to the Occupational Safety and Health Administration (OSHA) guidelines. The delivery of the TLT is expected to last 20 min total (simultaneous application on the left and right forehead). The subject will be asked to rest for five minutes after the delivery of TLT. The skin at the sites of the application will be inspected again prior to dismissing the subject. A log with the dates of treatment delivery per each study subject will be kept at MGH CATSD (Boston).

During TLT-DCS Visit 2-4, subjects will receive TLT-c (Visit 2), TLT-s (Visit 3) and TLT-p (Visit 4).

The following tasks will be completed prior to every TLT session:

- Utox
- Concomitant medications form
- ADVERSE EVENTS FORM
- ASQ (self-rated)
- SDQ (self-rated)
- NEURO-QoL (self-rated)
- SFI (self-rated)
- SAFTEE (self-rated)
- PANAS (self-rated)
- EEG- Recording
- DCS – Spectroscopy

The following tasks will be completed after every TLT session:

- DCS – Spectroscopy
- EEG- Recording
- Cognitive tests
- PANAS (self-rated)
- TSRQ (self-rated)
- PBQ (self-rated)

Subjects shall be instructed to contact the investigator or a member of his staff at any time between visits concerning adverse events or worsening of symptoms.

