4.12 Data Management

The principal investigator, [name] is ultimately responsible for the quality of the data collection and overall conduct of the study, and directly supervise the study coordinators and data management staff at MGH. Data management will include clinician and subject rated assessments (see assessments), screening data, fidelity data, visit adherence data and rater reliability data and safety reporting, including DCS and cognitive data. Weekly reports from REDCap will monitor subject enrollment, completion, attrition, and individual subject progress as well as the completion of critical assessments. Additional reports will be done as needed to monitor baseline characteristics, protocol adherence, and other issues of interest.

All measures that are completed on paper will be entered by the RA into REDCap, and a two pass verification system will be used to minimize any data entry errors. All records in REDCap have a form completion status that may be Incomplete (appears as a red circle in Record Status Dashboard), Unverified (yellow circle), or Verified. The RA initially entering data will save each record entered as Unverified (at which point it will appear as a yellow circle in the Record Status Dashboard). A second RA at each site will then go into each unverified record, compare each entered value against the paper source document, make any corrections, and then re-save the record as Verified (at which point it will appear as a green circle in the Record Status Dashboard). The color coding system built into REDCap readily allows for identification of unverified records.

Coded data may be sent to collaborators within and outside of Partners for research purposes. Coded sample/data may be shared with for profit companies that are working with Partners researchers, such as Litecure, LLC or Advanced Brain Monitoring, Inc (the manufacturer of the EEG device used this in study). Samples/data will not be sold to anyone for profit. Data may also be shared with other Partners IRB approved protocols supervised by the principle investigator of this study.

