4.14 Blinding of the Study

Since this is a single-blind, sham-controlled study, measures have been taken to assure that the integrity of the blinding of the treatment modalities remains intact. The two means of assuring that the treatment modalities will not be disclosed to subjects include detectors sensitive to heating of the skin (which will switch off the device to prevent overheating) and the introduction of a rating scale for subjects to assess their best guess on treatment assignment.

The performance/output of all visible and audible indicators is identical for all three treatment modalities, (i.e. other than the emission of invisible light radiation, the behavior of the system is identical for all).

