6.5 Protocol Adherence

The protocol must be read and followed by all participating study personnel.

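### Section 3.2 claims a blinded operator in a trial that blinds only subjects, and no masked processing is described for the DCS recordings behind the primary outcome

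*Combined protocol and SAP*

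**What the plan says.** Section 3.2 states that the apparent behaviour of the device in continuous, pulsed and sham mode "will be identical, ensuring the study is blinded to the operator". The next sentence of the same section calls the study single-blind.

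Everywhere else the plan blinds subjects only. Section 4.2 says "Only subjects will be blind to the treatment group assignment". Section 4.14 opens with "Since this is a single-blind, sham-controlled study", and the safeguards it lists concern disclosure to subjects. The Study Summary and the Data Collection Forms text under section 4.11 agree.

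The order is fixed. Section 4.2 says "While the sequence (c-TLT, s-TLT, p-TLT) will be the same for all subjects", and section 4.8.2 says "subjects will receive TLT-c (Visit 2), TLT-s (Visit 3) and TLT-p (Visit 4"). The schedule in the protocol attachments prints the mode by week. Section 6.5 adds "The protocol must be read and followed by all participating study personnel".

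On the primary outcome, section 5.5 says that delta CBF, from DCS before and after each session, is compared by paired t-test for p-TLT against c-TLT and for c-TLT against sham. It does not say who processes the recordings, by what rules, or with what knowledge of mode.

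On roles, section 4.8.2 says "The study PI will be an active participant in the delivery of the TLT". Section 4.12 has the same person "directly supervise the study coordinators and data management staff at MGH" and counts DCS data within data management.

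**The concern.** A reader of section 3.2 alone would credit the trial with a protection it lacks. That phrase is a small matter by itself. What matters more is that no other protection against knowledge of mode is described at the stage where one is still possible, namely the processing of the DCS signal into delta CBF.

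That processing leaves room for choice. Section 3.3 describes a probe with up to 8 detector fibre bundles at source-detector separations from 0.3 to 5 cm, and section 4.8.2 gives 10 minutes of DCS on each side of the session. Section 5.5 does not say which detectors or which part of the recording define delta CBF, or how artefacts are handled. Section 5.2 states the expected result in advance: p-TLT above c-TLT, and c-TLT above sham. Judgements made with the mode known and an order expected are a recognised route to bias, and these recordings feed both primary comparisons.

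**Working it through.** The plan gives no figure for this point to reproduce, so the check is mainly a comparison of passages, with one count.

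**Step 1: can the operator be blind?**
- Section 3.2: indicators are identical, so the console does not reveal the mode.
- Sections 4.2 and 4.8.2: every subject follows one order, with continuous light at Visit 2, sham at Visit 3 and pulsed light at Visit 4.
- Section 6.5: all personnel read the document that states this order.

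An operator who knows the visit number therefore knows the mode, whatever the console shows. Identical indicators can help to blind the subject. Under this order they cannot blind the operator.

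**Step 2: is masking supplied elsewhere?** Five places could have done so.
- Section 4.2: the device recognises subject codes generated by the statistician, but the same paragraph says that only subjects are blind.
- Data Collection Forms text under section 4.11: independent evaluators are mentioned for entering clinician-administered measures. They are not described as masked, nor as handling DCS.
- Section 4.12: coded data refers to sharing with collaborators.
- Section 4.14: both measures are aimed at the subject.
- Section 5.5: names the test and the comparisons only.

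None describes masked processing of DCS recordings.

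**Step 3: could the person processing the data know the mode?** The Data Collection Forms text says that the study database identifies data by subject number, visit number and visit date. The documents do not say how raw DCS files are labelled or who processes them. *Assumption:* the files carry the visit number or date, or can be linked to them. Then:
- sessions, if all ten subjects complete: 10 × 3 = 30;
- DCS recordings, before and after each session: 30 × 2 = 60;
- recordings whose mode follows from the visit number: 60 of 60.

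With a random code per session and with subject number, visit number and date removed, a guess among three equally frequent modes is right 1 time in 3, provided the signal itself does not reveal the mode.

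**Step 4: what can be said about direction?** The two comparisons are (p − c) and (c − s), where p, c and s are delta CBF under pulsed, continuous and sham mode. The continuous-mode value enters with opposite signs. A processing choice that raises it favours the second comparison and works against the first. Knowledge of mode therefore does not imply one direction of bias for both comparisons.

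**The case against.** The strongest reply is that the contradiction is one phrase in a device overview. The next sentence says single-blind, and the Study Summary and sections 4.2, 4.11 (Data Collection Forms) and 4.14 are explicit. A reader might infer that the plan is confused throughout about who is blind, or that it claims a double-blind design. The documents do not support that. Correcting the phrase alone changes no procedure and would be close to clerical.

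Second, the route to unmasking is partly assumed. The labelling rule concerns the study database, not raw DCS files, and nothing says that the principal investigator processes the signal. This stands, and the conclusion is conditional on it.

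Third, a reader might want to put a false-positive rate on the risk by simulating a choice among several detector signals. That would measure selection among undefined signals, which fixing the signal in advance removes without any masking. It would not measure the effect of mode-aware segment or artefact decisions. The result would also depend on how one signal serves two comparisons that share the continuous-light arm, and on a number of exchangeable signals that section 3.3 does not give. No inflation figure is claimed here.

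Fourth, a reader might infer that masking EEG processing also protects delta CBF. It does not, because section 5.5 derives delta CBF from DCS alone.

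Finally, masked processing leaves mode tied to visit order and leaves acquisition open. That is true and limits the benefit. It does not remove the case for masking the step that can be masked.

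**Conclusion.** The point holds in two parts. First, the operator-blinding claim in section 3.2 is inconsistent with section 4.2 and cannot be met under a fixed order that all personnel know. Second, the plan describes no masked processing of the DCS recordings behind its primary outcome, while it states an expected order and has the principal investigator both take part in delivery and supervise data management that includes DCS data.

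The consequence is a risk of bias in the section 5.5 comparisons, not a demonstrated bias. Its possible reach is all 60 recordings if ten subjects complete and if files can be linked to visit number or date. Its size and direction are not shown: the documents give no standard deviation or expected effect for delta CBF and no description of the processing. Confidence is high for the contradiction and the omission. The plan should be changed before any DCS data are processed, because the remedy is cheap then and cannot be fully recovered afterwards.

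**What to change.** 1. In section 3.2, replace the operator phrase with wording that agrees with the single-blind statements in the Study Summary and sections 4.2, 4.11 (Data Collection Forms) and 4.14. State that acquisition is not masked.
2. Add to section 5.5:
   - before processing, an existing team member who does not process the data replaces subject number, visit number and date on each DCS file with a random session code that keeps the before and after recordings paired;
   - rules for detector selection, segment and artefact rejection are fixed in advance;
   - delta CBF for all sessions is locked before codes are linked to mode.
3. Optionally, apply the same coding to EEG files, to protect the EEG endpoint and its correlation with the change in CBF.

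The cost is one wording change, a short written rule, and the recoding of up to 60 DCS recordings. The documents do not identify the person who would hold the codes, so the plan must name the role. No visits, subjects or devices are added, and the order of sessions is unchanged. Staff will still know the mode during the session, and mode remains confounded with visit order.
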